3.2 Primary Study Endpoints

Exercise capacity assessed by peak oxygen consumption (VO₂) achieved during exercise testing will be the primary endpoint for Aim 1. Chronic activity levels assessed by accelerometry will be the primary endpoint for Aim 2. Assessments were performed after 12 weeks of intervention.

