Diagnosis and Main Inclusion Criteria	
Heart failure with preserved ejection fraction (HFpEF) defined by clinical heart failure, normal EF ($\geq 50\%$) and at least one of the following:
 
 • Previous hospitalization for HF with radiographic evidence (pulmonary venous hypertension, vascular congestion, interstitial edema, pleural effusion) of pulmonary congestion or • Catheterization documented elevated filling pressures at rest or with exercise or • Elevated NT-proBNP (>400 pg/ml) or • Echo evidence of diastolic dysfunction/elevated filling pressures manifest by medial E/e' ratio ≥ 15 and/or left atrial enlargement and chronic treatment with a loop diuretic for signs or symptoms of heart failure
Study Product, Dose, Route, Regimen	
Stage I tested Inhaled, nebulized sodium nitrite (AIR001) 80 mg at least 4 hours apart three times daily during waking hours (i.e. 08:00, 12:00, 16:00).
 
Stage II is testing oral nitrite 40 mg tid capsules vs matching placebo capsules (same dosing frequency).

Duration of Administration	12 weeks
Reference therapy	Placebo
Statistical Methodology	Data will be analyzed according to ITT principles (assigned group regardless of study drug administration or compliance with ET benchmarks achieved). Primary hypotheses will be tested using a two-sample t-test on the change (baseline to 12 week). Testing will be stratified by route of administration.

1 Introduction

Heart failure with preserved ejection fraction (HFpEF) afflicts millions of older Americans and is associated with exercise intolerance, reduced quality of life (QOL), high health care costs, and increased mortality. People with HFpEF display increased cardiac filling pressures and inadequate cardiac output reserve to deliver blood to the body during exercise. Numerous lines of evidence have implicated abnormalities in nitric oxide-cyclic guanosine monophosphate (NO- cGMP) signaling as playing a key role in promoting these abnormalities. While there is currently no proven effective medical treatment for HFpEF, exercise training (ET) has been shown to improve aerobic capacity and QOL in this population.

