- Our **primary hypothesis** is that combination of NO₂⁻ and ET will be associated with greater improvement in daily activity levels compared to ET with placebo. Our **secondary hypotheses** are that combination of NO₂⁻ and ET will be associated with improvement in symptoms of dyspnea and fatigue, improved tolerability to ET, enhanced endothelial function and better QOL compared to ET with placebo.

3 Study Design

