7.1 Statistical Overview

7.2 The full statistical details for this protocol are documented in the supplementary Statistical Analysis Plan (SAP). This protocol provides the key information, namely the justification for the sample size and the details on the primary analysis. The details regarding secondary endpoints, subgroup analyses, missing data and analysis sets are provided in the SAP. **Sample Size Determination**

In the RELAX trial, the mean \pm SD change in peak VO₂ with placebo in subjects with HFpEF treated for 6 months was 0 ± 2.0 ml/kg/min,³⁶ and in a previous trial of ET in HFpEF, the increase in peak VO in the ET arm was $+2.3\pm 2.2$ ml/kg/min.²² An increase of 75% (additional 1.5 ml/kg/min) in this change would be considered clinically relevant. Thus, we estimate that a sample size of N=34 participants per group will be required to provide 80% statistical power (two-tailed, alpha=0.05) to detect the difference of 1.5 ml/kg/min between subjects randomized to NO₂⁻ with ET versus placebo with ET. To account for attrition, we will increase our number of randomized subjects to 40/group (enroll 80 subjects total to accrue 68 total or 34 in each group).

Stage 1 was discontinued early because of loss of inhaled nitrite availability, therefore we will accrue a total of 68 patients with complete data combining the patients with complete data receiving inhaled placebo in Stage I (n=17) with another 51 patients in Stage II (17 receiving placebo and 34 receiving nitrite) to ensure that the study is adequately powered to test the study hypotheses.

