7.3 Primary Outcome Analysis

Primary Statistical Hypotheses:

H0: Change from baseline to 12 weeks in Peak VO₂ in participants randomized to NO₂⁻ will be equal to the change in Peak VO₂ in participants randomized to placebo.

Ha: The change from baseline to 12 weeks in Peak VO₂ will be different between the two randomized groups

Analysis Summary:

The primary statistical hypothesis will be tested using a regression framework. The dependent variable will be the change (baseline to 12 week) in Peak VO₂. An indicator variable will be used to indicate the randomized treatment assignment (NO₂⁻ vs. placebo as the referent). This analysis is equivalent to a two-sample t-test. While the study design is randomized, the number of participants is relatively small, so imbalance between putative confounding variables may be observed. To address this, we will conduct an a priori sensitivity analysis that will adjust for baseline Peak VO₂, BMI, Sex, and Age group strata through an extension of the regression model used for the primary analysis. The type III estimate of the treatment effect will be compared to the unadjusted estimate to assess the robustness of the randomization process.

Statistical testing for the primary analysis will be two-sided at the alpha=0.05 level of significance.

8 Safety and Adverse Events

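### Two endpoints are labelled primary, but hypotheses and alpha are written for peak VO2 only and no rule links the two; if either can win at 0.05, family-wise error is about 8–10%

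*Combined protocol and SAP*

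**What the plan says.** **Two primary endpoints.** Protocol section 3.2 says that peak VO2 "achieved during exercise testing will be the primary endpoint for Aim 1", and continues: "Chronic activity levels assessed by accelerometry will be the primary endpoint for Aim 2". Neither is ranked above the other. Section 2 matches this. Aim 1 has a primary hypothesis on peak VO2. Aim 2 has a primary hypothesis that nitrite plus training "will be associated with greater improvement in daily activity levels compared to ET with placebo".

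**The tests.** The Study Summary, under Statistical Methodology, says: "Primary hypotheses will be tested using a two-sample t-test on the change (baseline to 12 week" (the parenthesis closes there). It gives no alpha. Section 7.3 states one null and one alternative hypothesis, both for change in peak VO2 from baseline to 12 weeks, and ends: "Statistical testing for the primary analysis will be two-sided at the alpha=0.05 level of significance". The sample size paragraph in section 7 also rests on peak VO2 alone, with 34 per group "to provide 80% statistical power (two-tailed, alpha=0.05").

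**What links them.** No alpha, model or place in a testing order is given for accelerometry, and there is no success rule across the two endpoints. Section 7 refers to a separate SAP for full statistical detail. The topics it names for that document are secondary endpoints, subgroups, missing data and analysis sets. It says that the protocol itself carries the detail of the primary analysis. Reference 63 is a paper on a Bonferroni-type correction for correlated endpoints; the body of the protocol does not cite it.

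**The concern.** Both endpoints ask whether nitrite adds to exercise training, and both are measured in the same patients. With two primary labels and no linking rule, the analyst can choose after seeing the data which endpoint carries the claim. A significant accelerometry result beside a null peak VO2 result could be presented as a positive primary outcome, and nothing in sections 2, 3.2 or 7.3 would contradict that. The 0.05 in 7.3 would then not describe the chance of a false primary claim.

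**Working it through.** **Inputs**

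- Two-sided alpha 0.05, from sections 7.2 and 7.3. It is the only significance level in the text.
- Difference of 1.5 ml/kg/min in peak VO2, 80% power and 34 per group, from the sample size paragraph.
- SD of change 2.2 ml/kg/min, from the earlier exercise training trial quoted there. The same paragraph gives 2.0 for the placebo arm of the sildenafil trial.
- Correlation between the two test statistics: not given anywhere, so a range is assumed.

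**Step 1: reproduce the plan's figure.** n per group = 2 × (1.960 + 0.842)² × (2.2 / 1.5)² = 2 × 7.85 × 2.151 = 33.8, so 34. Power at 34 per group is 80.3% (79.1% by the exact t-test). An SD of 2.0 would give 28, so 2.2 is the SD behind the figure. The plan's 34 per group is therefore sized for one test, peak VO2, using the whole 0.05.

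**Step 2: error if either endpoint can win.** Assume that both are tested at two-sided 0.05 and that one significant result is enough.

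- Independent tests: 1 − (1 − 0.05)² = 1 − 0.9025 = 9.75%.
- Correlated tests: 1 − P(|Z1| < 1.96 and |Z2| < 1.96) for a bivariate normal pair with correlation ρ.

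| ρ (assumed) | At least one false positive |
|---|---|
| 0 | 9.75% |
| 0.3 | 9.5% |
| 0.5 | 9.1% |
| 0.7 | 8.35% |
| 0.75 | 8.1% |
| 0.8 | 7.8% |
| 0.9 | 7.0% |

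**Step 3: error if peak VO2 alone is confirmatory.** One test at 0.05 has an error of 5%.

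**Step 4: compare two remedies.**

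- *Fixed sequence, peak VO2 then accelerometry, each at 0.05.* If nitrite has no effect on peak VO2, any false claim has to pass that test first, so the error is at most 5%. If nitrite does affect peak VO2, the only possible false claim is on accelerometry, again at most 5%. The 34 per group and 80.3% power for peak VO2 stay as they are.
- *Equal split, 0.025 each.* For independent tests the error is 1 − 0.975² = 4.94%, and it is lower with correlation. Peak VO2 would then need 2 × (2.241 + 0.842)² × 2.151 = 40.9, so 41 per group (43 by the t-test). At 34 per group its power falls to 71.6% (69.7% by the t-test).

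**The case against.** The strongest reply is that section 7.3 already settles the matter. It writes hypotheses for peak VO2 only, the sample size uses peak VO2 only, and the 0.05 belongs to that analysis, so on this reading the error is 5%. This is a fair reading of 7.3, but sections 2 and 3.2 do not support it: they give accelerometry the same primary status without qualification.

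Three stronger readings are tempting, and the documents support none of them.

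- *Both endpoints are each tested at 0.05.* A reader might infer this from 0.05 being the only level given, but no alpha is stated for accelerometry. The plural in the Study Summary does not prove two confirmatory tests either, since 7.3 uses a plural heading for the hypothesis pair of a single endpoint.
- *The plan has no multiplicity rule.* This can be said only of the text reviewed. The SAP is cited for full detail and may hold a rule. Reference 63 does not decide it: references 1–3 and 62 are also uncited in the body, and the entry fits equally well with a correction described in a fuller document. What remains is that section 7 assigns the primary analysis to the protocol and does not list multiplicity among the SAP's topics.
- *The plan promises 5% for the trial as a whole and breaks that promise.* No trial-wide error rate is stated anywhere.

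It can also be argued that separate aims in a single-site Phase II trial need no joint error control. That is a defensible position, but the plan would have to state it, because it determines what a significant accelerometry result may be called.

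**Conclusion.** The point holds in conditional form. Two endpoints carry the primary label, only one has hypotheses and an alpha, and nothing in the available text connects them.

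The inflation to 9.75% (independent tests), or to about 8% or more for correlations up to about 0.75, rests on two assumptions that the documents neither state nor exclude: that accelerometry is tested at two-sided 0.05, and that success on either endpoint is enough. Above a correlation of 0.75 the figure is lower, 7.0% at 0.9. With peak VO2 as the sole confirmatory endpoint it is 5%. The defect is that the plan as written allows either reading, so the choice could be made once results are known. It should be corrected before analysis. It does not affect the validity of the peak VO2 test itself.

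**What to change.** In sections 3.2 and 7.3, and in the SAP to match, state that:

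1. peak VO2 is tested first at two-sided 0.05, as the sample size and 7.3 already assume;
2. accelerometry is tested second at two-sided 0.05 in fixed sequence, with a confirmatory claim only if peak VO2 is significant;
3. otherwise accelerometry is reported as supportive.

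If the SAP already contains a multiplicity rule, put that rule into 7.3 instead.

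The cost is a few sentences. Sample size and power for peak VO2 are unchanged, whereas an equal alpha split would lower that power or require more patients in a trial that, by section 1.0, already cannot meet its earlier recruitment goal. The one downside of the fixed sequence is that accelerometry has no stand-alone confirmatory claim if peak VO2 is not significant.

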3.3 Secondary Study Endpoints

Cardiac output reserve, peak exercise workload, rest and exercise hemodynamics assessed by echocardiography, Borg dyspnea and fatigue scores recorded during ET, endothelial function assessed by tonometry, QOL assessed by the Kansas City Cardiomyopathy Questionnaire and body composition assessed by dual energy X-ray absorptiometry (DEXA). Cardiac structure and function will be assessed by cardiac MRI and adipose content will be assessed by MRI in subjects participating in the optional MRI substudy. The muscle biopsy will tell us about what improvements we see in the leg muscles, and specifically in the mitochondria of leg muscles.

There will be ancillary trial endpoints to assess QOL, Borg symptom scores, DEXA, AXM data, and exercise capacity following completion of the main trial, comparing subjects randomized to usual care or behavioral/motivation intervention.

3.4 Primary Safety Endpoints

Safety endpoints will include blood pressure, methemoglobin levels, symptoms of dizziness, lightheadedness, headaches, and cough.

4 Subject Selection Enrollment and Withdrawal

4.1 Inclusion Criteria

1. Age \geq 40 years
2. Symptoms of dyspnea (II-IV) without evidence of a non-cardiac or ischemic explanation for dyspnea
3. EF of $>$ or $=$ 50% determined on most recent imaging study within the preceding 5 years, with no change in clinical status suggesting potential for deterioration in systolic function
4. One of the following:

- Previous hospitalization for HF with radiographic evidence (pulmonary venous hypertension, vascular congestion, interstitial edema, pleural effusion) of pulmonary congestion **or**

- Catheterization documented elevated filling pressures at rest (PCWP ≥ 15 or LVEDP ≥ 18) or with exercise (PCWP ≥ 25) **or**
- Elevated NT-proBNP (>400 pg/ml) or BNP(>200 pg/ml) **or**
- Echo evidence of diastolic dysfunction/elevated filling pressures manifest by medial E/e' ratio ≥ 15 and/or left atrial enlargement **and** chronic treatment with a diuretic for signs or symptoms of heart failure

5. Heart failure is primary factor limiting activity as indicated by answering # 2 to the following question:

My ability to be active is most limited by:

1. Joint, foot, leg, hip or back pain
2. Shortness of breath and/or fatigue and/or chest pain
3. Unsteadiness or dizziness
4. Lifestyle, weather, or I just don't like to be active

6. No chronic nitrate therapy or not using intermittent sublingual nitroglycerin (requirement for >1 SL nitroglycerin per week).

7. No daily use of phosphodiesterase 5 inhibitors or soluble guanylyl cyclase activators and willing to withhold prn use of phosphodiesterase 5 inhibitors for duration of study

8. Ambulatory (not wheelchair / scooter dependent)

9. Body size allows wearing of the accelerometer belt as confirmed by ability to comfortably fasten the test belt provided for the screening process

10. Willingness to wear the accelerometer belt for the duration of the trial

42 Exclusion Criteria

1. Recent (< 1 month) hospitalization for heart failure
2. Ongoing requirement for PDE5 inhibitor, organic nitrate or soluble guanylyl cyclase activators
3. Hemoglobin (Hgb) < 8.0 g/dl within 30 days prior to randomization
4. GFR < 20 ml/min/1.73 m² within 30 days prior to randomization
5. Systolic blood pressure < 115 mmHg seated or < 90 mmHg standing
6. Resting HR > 110
7. Previous adverse reaction to the study drug which necessitated withdrawal of therapy
8. Significant chronic obstructive pulmonary disease that is a primary contributor to symptoms in the opinion of the investigator
9. Ischemia thought to contribute to dyspnea in the opinion of the investigator
10. Documentation of previous EF $< 40\%$
11. Acute coronary syndrome within 3 months defined by electrocardiographic (ECG) changes and biomarkers of myocardial necrosis (e.g., troponin) in an appropriate clinical setting (chest discomfort or anginal equivalent)
12. PCI, coronary artery bypass grafting, or new biventricular pacing within past 3 months
13. Obstructive hypertrophic cardiomyopathy
14. Known infiltrative cardiomyopathy (amyloid)

15. Constrictive pericarditis or tamponade
16. Active myocarditis
17. Complex congenital heart disease
18. Active collagen vascular disease
19. More than mild aortic or mitral stenosis
20. Intrinsic (prolapse, rheumatic) valve disease with more than moderate mitral, tricuspid or aortic regurgitation
21. Acute or chronic severe liver disease as evidenced by any of the following: encephalopathy, variceal bleeding, INR > 1.7 in the absence of anticoagulation treatment
22. Terminal illness (other than HF) with expected survival of less than 1 year
23. Enrollment or planned enrollment in another therapeutic clinical trial in next 3 months.
24. Inability to comply with planned study procedures
25. Pregnancy or breastfeeding mothers

4.3 Subject Recruitment, Enrollment and Screening

Eligible patients will be identified from screening of the inpatient and outpatient heart failure services of the Mayo Clinic in Rochester, Minnesota. As well as the cardiovascular medicine and general medical services of the Mayo Clinic Health Systems. Patients that participated in the first stage (with inhaled nitrite) will also be eligible to participate in the second stage with oral nitrite, provided that at least 6 months have passed since the first exercise training intervention. Data from the same patients in different phases will not be analyzed together, but rather separately.

Eligible patients will be paid up to \$500 if the entire study is completed. If they are not able to complete the entire study, they will be paid as follows for the study visits they do complete: \$100 each for completion of Visits 1 & 4, \$50 each for Visits 2 & 3 and \$5 for each cardiac rehab session completed.

Patients will also be given a 6 hour parking pass for the screening visit, final visit and visits at week 4, 8 and 12.

4.4 Early Withdrawal of Subjects

4.4.1 When and How to Withdraw Subjects

Development of any condition that requires study withdrawal related to safety, disease progression, subject decision or failure to adhere to protocol requirements could qualify as reason to withdraw for the study.

4.4.2 Data Collection and Follow-up for Withdrawn Subjects

Subjects withdrawing from the study will be contacted 2 weeks following last dose of study drug to ensure that there have been no adverse events. Participants that withdraw may be replaced to allow for achievement of target enrollment.

5 Study Drug

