6.4 Final Visit

The Final Visit of the drug interventional part of the study for Stage I occurred at week 12

This visit will include all of the assessments performed in Screening Visit 1 (see above). Participants will be asked not to take their study medications the day of this visit; they will be asked to administer a treatment directly prior to the final visit CPET under direct investigator observation. For Stage I, inhaled study drug was administered immediately prior to CPET. For Stage II, oral study drug is administered (under direct observation by study staff) 30 minutes prior to CPET. AXM data will be downloaded and devices returned or changed out. Participants will return all other study materials at the final visit and all unused study drug.

At the Final ET Visit (week 12), participants will be offered enrollment in an ancillary study to evaluate the effects of behavioral/motivational intervention on chronic activity levels and QOL. Subjects agreeing to this part of the trial will then be randomized to behavioral/motivational intervention (motivational phone calls twice weekly with one investigator visit per week) or standard care (no additional contact). Participants will continue to wear AXM devices following this visit to assess how well increases in chronic activity levels are maintained following ET intervention. Involvement in this part of the trial is optional.

Study subjects not participating in the ancillary study will be contacted by phone 2 weeks following the final ET visit (week 12) to verify that there have been no adverse events.

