Measurement of QOL will be performed every other week at ET sessions using the Kansas City Cardiomyopathy Questionnaire (KCCQ).^{56, 57} The KCCQ score reflects clinical status in HF with high fidelity;^{56, 57} the score changes rapidly with clinical improvement or deterioration,^{58, 59} is strongly associated with outcome,⁶⁰ and performs equally well in HFpEF and HFrEF.⁶¹ The SF36 will be completed at the screening visit and final endpoint visit (week 12).

Endothelial function will be assessed at Visit 1 and Visit 2 using digital arterial tonometry (reactive hyperemia peripheral arterial tonometry, RH-PAT, EndoPAT, Itamar Medical).⁹ These noninvasive assessments are routinely performed for both research and clinical care purposes. Changes in activity level, QOL and symptoms will then be correlated with changes in microvascular endothelial function (RH-PAT).

Assessment of Exercise capacity will be performed at Visit 1 (pre drug) and Visit 2 (week 10 for Stage II of study) using expired gas analysis in the laboratory of [name] (Joseph 4).

Subjects participating in the additional ancillary study will also undergo an additional cardiopulmonary exercise test at the final ancillary study visit. Participants will undergo standard, maximal effort cardiopulmonary testing on a semi-recumbent cycle ergometer to maximal subjective effort level with assessments of gas exchange as described below:

- Measurement of Gas Exchange and Ventilation will be performed during exercise testing to measure the volumes of VO₂, carbon dioxide produced (VCO₂), breathing frequency (fb), tidal volume (VT), minute ventilation (VE), partial pressure of end-tidal oxygen and carbon dioxide (PETO₂ and PETCO₂), and derived variables (e.g., respiratory exchange ratio, VE/VCO₂, etc.) using a low resistance, open circuit, automated metabolic system (Medical Graphics Co., St. Paul, MN) integrated to a mass spectrometer (Perkin Elmer, model 1100) as we have previously described.^{4,9,13,35,36}
- Cardiac Output (CO) will be measured at rest and during exercise by the acetylene (C₂H₂) wash-in technique first described by Stout et al., refined by Gan et al. and Nielson et al. and validated against direct Fick in our laboratory.⁴⁵⁻⁴⁸

Echocardiography will be performed at rest and during exercise at Visit 1 and Final Visit to estimate central cardiac hemodynamics and ventricular function, including EF, Doppler-estimated pulmonary artery systolic pressure, and LV filling pressures (E/e' ratio).

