9.1 Confidentiality

Information about study subjects will be kept confidential and managed according to the requirements of the Health Insurance Portability and Accountability Act of 1996 (HIPAA). Those regulations require a signed subject authorization informing the subject of the following:

- What protected health information (PHI) will be collected from subjects in this study
- Who will have access to that information and why
- Who will use or disclose that information
- The rights of a research subject to revoke their authorization for use of their PHI.

In the event that a subject revokes authorization to collect or use PHI, the investigator, by regulation, retains the ability to use all information collected prior to the revocation of subject authorization. For subjects that have revoked authorization to collect or use PHI, attempts should be made to obtain permission to collect at least vital status (long term survival status that the subject is alive) at the end of their scheduled study period.

92 Source Documents

Source data is all information, original records of clinical findings, observations, or other activities in a clinical trial necessary for the reconstruction and evaluation of the trial. Source data are contained in source documents. Examples of these original documents, and data records include: hospital records, clinical and office charts, laboratory notes, memoranda, subjects' diaries or evaluation checklists, pharmacy dispensing records, recorded data from automated

instruments, copies or transcriptions certified after verification as being accurate and complete, microfiches, photographic negatives, microfilm or magnetic media, x-rays, subject files, and records kept at the pharmacy, at the laboratories, and at medico-technical departments involved in the clinical trial.

93 Case Report Forms

The study case report form (CRF) is the primary data collection instrument for the study. All data requested on the CRF will be recorded. All missing data will be explained.

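### ITT is declared whatever the compliance, but the protocol asks no patient who stops early to attend the week-12 peak VO2 test

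*Combined protocol and SAP*

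**What the plan says.** - **Analysis principle** (Study Summary, Statistical Methodology): "Data will be analyzed according to ITT principles (assigned group regardless of study drug administration or compliance with ET benchmarks achieved".
- **Grounds for withdrawal** (4.4.1): "safety, disease progression, subject decision or failure to adhere to protocol requirements could qualify as reason to withdraw for the study". The sentence opens by speaking of conditions that require withdrawal and ends permissively, so withdrawal for non-adherence is possible but discretionary.
- **What follows withdrawal** (4.4.2): "Subjects withdrawing from the study will be contacted 2 weeks following last dose of study drug to ensure that there have been no adverse events". The next sentence is "Participants that withdraw may be replaced to allow for achievement of target enrollment". No efficacy assessment is mentioned, although the section heading covers data collection.
- **Revoked authorization** (9.1): "attempts should be made to obtain permission to collect at least vital status". This yields no peak VO2.
- **Primary variable** (7.3): change in peak VO2 from baseline to 12 weeks. It comes from "maximal effort cardiopulmonary testing on a semi-recumbent cycle ergometer to maximal subjective effort level" (Study Assessments), done at the first and final visits.
- **Final visit** (6.4): "they will be asked to administer a treatment directly prior to the final visit CPET under direct investigator observation". Patients who have already stopped study drug are not addressed. The Schedule of Assessments (15.1) has no early-termination column.
- **Payment** (4.3): "If they are not able to complete the entire study, they will be paid as follows for the study visits they do complete". The list includes a Visit 4, which may be the final visit.
- **Accrual** (1.0 and 7.2) is counted in patients with complete data: 51 in Stage II, plus 17 inhaled-placebo patients from Stage I.
- **Missing data and analysis sets** are deferred by 7.1 to a supplementary SAP whose text is not in the supplied file.

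**The concern.** An ITT comparison needs the outcome as well as the assignment. The Summary says poor compliers count in their assigned group. Sections 4.4.1 and 4.4.2 allow such a patient to leave the study and be replaced, with no request for the one measurement that the primary analysis uses. Replacement restores the count of complete cases but not the lost outcome.

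The losses may be informative. Section 1.1 hypothesises that nitrite improves tolerance of and adherence to training. Section 1.4 reports two withdrawals for hypotension in a separate oral nitrite study of older heart failure patients. Pointing the other way, 1.0 says oral drug has been very well tolerated in the 14 patients enrolled so far. If leaving the study depends on both treatment and prognosis, a comparison of those who remain no longer answers the declared question. A test not done at week 12 cannot be done later.

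**Working it through.** **1. The plan's own sample size.** Inputs from 7.2: difference 1.5 ml/kg/min, SD of change 2.2 (exercise-training arm of the cited trial), two-sided alpha 0.05, power 80%.

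n per group = 2 × (1.960 + 0.842)² × 2.2² / 1.5² = 33.8, so 34. Inflating for 15% loss gives 34 / 0.85 = 40. Both stated figures reproduce. The concern disputes neither.

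**2. The plan's allowance for incomplete data, all causes.**
- Original 1:1 plan (7.2): 80 − 68 = 12, and 12/80 = 15.0%.
- Stage II: at most 64 (Study Summary) against 51 with complete data (7.2). 64 − 51 = 13, and 13/64 = 20.3%.
- Section 1.0 would give 60 − 47 = 13, and 13/60 = 21.7%. I do not rely on this. With 51 needed and 14 enrolled, 51 − 14 = 37, not 47, and 14 + 60 = 74 exceeds the Summary's 64.

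These are planning allowances, not observed losses. The share due to non-adherence is not given.

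**3. Following an early stopper through the text.**
- *Stops drug or training but is not withdrawn.* No section says this patient leaves, and none says the patient is asked to attend week 12. Section 6.4 presents the final exercise test with an observed dose beforehand.
- *Withdrawn for non-adherence, still consenting.* Section 4.4.2 provides the safety contact and possible replacement. No exercise test is requested.
- *Revokes authorization.* Section 9.1 seeks vital status. No change in wording could oblige this patient to be tested.
- *Poor complier who attends week 12.* Analysed as assigned. There is no problem.

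The gap is therefore in the first two rows.

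**4. Why no bias figure follows.** Let d be the fraction in an arm without a week-12 value, and x the mean change in completers minus the mean change that the others would have shown. The arm's all-randomised mean is the completer mean minus d·x. The completer difference (nitrite minus placebo) then departs from the all-randomised difference by

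d(nitrite)·x(nitrite) − d(placebo)·x(placebo).

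The documents give only an overall allowance for d, not split by arm, and nothing on x. Neither sign nor size can be stated.

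**5. Reach of any remedy.** Stage I is complete. Of the 34 planned placebo patients, 17 (half) come from Stage I and are counted because their data are complete. New wording cannot change that half.

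**The case against.** The strongest reply is that nothing forbids the test. Section 4.4.2 sets a safety contact without barring a final visit, and 4.3 pays non-completers for visits they make. Several provisions keep imperfect adherers in: dose reduction and restart (5.1), mailing drug to patients who miss visits (5.9.3), and modified home exercise (6.2). Withdrawal for non-adherence is discretionary. Replacement is an accrual rule and removes nobody from analysis. Analysis sets and missing data belong to a SAP that was not available.

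All of this stands, and it rules out stronger readings that a reader might infer:
- *The primary outcome cannot be observed in withdrawn patients.* The text supports only that it is not requested.
- *The trial will be analysed in completers, or replacement drops patients.* The rules that would settle this are in the SAP, so no such claim is made.
- *The nitrite effect will be exaggerated.* No direction follows from the documents.
- *Accelerometry is safer because devices are downloaded at weeks 4 and 8.* Section 3.2 places both primary endpoints after 12 weeks, and nothing lets an earlier download stand in.

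What the reply leaves untouched is collection. Permission and payment are not a request to attend, and a SAP rule can model a missing week-12 value but cannot obtain it.

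**Conclusion.** The point holds as a gap in data collection. The protocol declares ITT irrespective of compliance, allows withdrawal for non-adherence, and nowhere asks patients who stop early and still consent to take the week-12 exercise test. Possibly informative primary outcomes may therefore go uncollected. The scale available is the plan's own allowance of 15% (original plan) to 20% (Stage II maximum) for incomplete data of every kind. Only an unknown part of that concerns early stoppers who could still be tested. No size or direction of bias is claimed. The conclusion rests on the supplied protocol text and assumes nothing about the SAP. It is worth correcting because the remedy uses a visit already planned and the value cannot be recovered afterwards.

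**What to change.** For Stage II patients still to complete:

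1. In 4.4.1 and 4.4.2, separate stopping study drug or training from leaving the study, and do not end outcome follow-up solely for non-adherence. Decisions on stopping drug or training stay as they are.
2. Ask randomised patients who stop early, still consent and are judged by the investigator able to be tested to attend the planned week-12 assessment.
3. Reconcile this with 6.4, where the final exercise test follows an observed dose and patients off drug are not addressed. No dosing rule is proposed here.
4. State that added patients do not displace withdrawn ones, who remain in their assigned group, and say whether patients retrieved in this way count toward the 51.
5. Check that the SAP's analysis set and missing-data rules agree, and that it has a sensitivity analysis not assuming missing at random.

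**Cost.** Wording in three sections, a SAP check, and at most 13 final visits on the 64-against-51 allowance, fewer once patients who withdraw consent or cannot be tested are excluded.

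Some dilution follows, which the declared ITT question accepts. As an illustration on assumption, take the original 40 per group, all measured, with 15% of the nitrite arm having no drug effect. The difference becomes 1.5 × 0.85 = 1.275, and t-test power is 72.6% (SD 2.2) or 80.4% (SD 2.0). For comparison, power is 79.1% for 34 per group at 1.5 and SD 2.2.

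The 17 pooled Stage I placebo patients remain completers only, while Stage II would gain off-treatment tests. The analysis should acknowledge that asymmetry.
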